5.4 Duration of Therapy

In the absence of treatment delays due to adverse events, treatment may continue for a total of 104 weeks in all from the start of study therapy or until one of the following criteria apply:

- Disease progression as defined in Section 7.0
- Inter-current illness that prevents further administration of treatment
- Unacceptable adverse event(s)
- Patient voluntarily withdraws from treatment
- General or specific changes in the patient's condition render the patient unacceptable for further treatment in the judgment of the investigator

Do not hold scans, continue scan schedule every 12 weeks from cycle 5 day 1 regardless of treatment delays thereafter.

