5.6 Duration of Follow-Up

Patients will be followed every 3 months for 24 months after removal from treatment or until death, whichever occurs first. Patients removed from treatment for unacceptable adverse events will be followed until resolution or stabilization of the adverse event.

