6.0 STUDY PROCEDURES

6.1 SCHEDULE OF ASSESSMENTS:

	Screening (within 28 days)	C1D1	C2D1	C3D1	C4D1	D1C5+	EOT¹²	Follow Up⁸
Informed Consent	X							
Review Eligibility Criteria	X							
Demographics, Height	X							
Prior and Concomitant Medications	X	X	X	X	X	X	X	
Review Adverse Events¹⁰	X	X	X	X	X	X	X	
Physical Examination, Vital Signs¹, Weight	X	X	X	X	X	X	X	
ECOG Performance Status	X	X	X	X	X	X	X	
Survival Status								X Q3m
Laboratory Assessments								
Pregnancy Test for WOBCP²	X							
CBC with diff, platelets³	X	X	X	X	X	X	X	
Comprehensive Metabolic Panel, including Alk Phos⁴	X	X	X	X	X	X	X	

	Screening (within 28 days)	C1D1	C2D1	C3D1	C4D1	D1C5+	EOT ¹²	Follow Up ⁸
LDH	X	X	X	X	X			
PSA¹¹	X	X	X	X	X	X	X	X
Testosterone¹¹	X				X		X	
TSH, free T3, free T4 (If Clinically Indicated: FSH, LH, ACTH)	X	X	X	X	X	X ⁶	X	
Therapy								
Cohorts A and B Nivolumab 3 mg/kg IV q3 wks for up to 4 doses¹³				X				
Cohorts A and B Ipilimumab 1 mg/kg IV q3 wks for up to 4 doses¹³				X				
Cohorts A and B Nivolumab 480 mg IV q4 wks for up to 23 doses¹³						X		
Cohort C Nivolumab 480 mg IV q4 wks¹⁴				X		X		
Imaging Tumor Assessments								
CT chest	X					X (q 12 wks)		
CT Abdomen/Pelvis or MRI Abdomen/Pelvis⁵	X					X (q 12 wks)		
Tc^{99m} Bone Scan (prostate only)	X					X (q 12 wks)		
QoL: BPI-SF and EORTC QLQ C30	X					X (q 12 wks)		
Correlatives								
Tumor Tissue Archival (CRPC preferred if available)	X							
Tumor Biopsy	X						X ⁷	
Research blood⁹		X	X	X		X (q 12 wks)	X	

1. Vital signs will include temperature, pulse, respirations, blood pressure; height will be obtained at screening only.
2. WOCBP: Women of child bearing potential; urine or serum pregnancy test.
3. CBC with diff includes total WBC, hemoglobin, hematocrit and differential of the WBC including absolute counts.
4. COMP or Comprehensive metabolic profile includes sodium, potassium, chloride, bicarbonate, BUN, creatinine, AST, ALT, alkaline phosphatase, total bilirubin.
5. With or without intravenous contrast, before or on associated visit. CT or MRI (preferred) brain with or without IV contrast if suspected or known brain metastases. Frequency of tumor assessments will be q12 weeks.
6. Every 42 calendar days ± 14 business days. May be delayed if infusion is not scheduled within the window.
7. Optional tissue biopsy collection at progression if subject consents; +/- 14 working days.
8. Follow up with phone call or with clinic visit.

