9. Blood for research should be collected prior to study treatment on C1D1, C2D1, C3D1 and C5D1, every 12 weeks thereafter and end of treatment.

10. Data on adverse events will be collected from the time of the initial study drug administration through 100 days after the last dose of study drug (nivolumab and/or ipilimumab) as described in Section 8.2.
11. For Cohort A only
12. End of Treatment Visit should occur within 3-4 weeks of last dose of protocol therapy.
13. Cohorts A and B (Nivolumab and Ipilimumab: 1 cycle (C) = 21 days (D) for up to 4 doses of Nivolumab (3mg/kg IV) and Ipilimumab (1mg/kg IV), then Nivolumab maintenance therapy alone (480mg IV): 1 cycle=4 weeks or 28 days (D). Total treatment time is up to 104 weeks.
14. Cohort C (Nivolumab monotherapy): 1 cycle (C) = 28 days (D) of Nivolumab monotherapy (480mg IV) for up to 104 weeks.

NOTE:

All procedures in study assessments schedule have a window of \pm 3 business days unless otherwise mentioned. Virtual clinic visits will be allowed per clinician/ subject discretion.

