Quality of Life (QoL) in subjects treated on protocol therapy will be described using EORTC-QLQ-C30 and BPI-SF measures. Baseline will be described using means or medians with an associated variance statistic. Change from baseline will be reported at each time point thereafter with similar descriptive statistics. Each measure will be reported for the overall population and separately by cohort. Each QoL change from baseline will be analyzed using a general linear model with repeated measures for an association with response.

Exploratory Endpoint Analysis

Tumor genome profiling by integrated DNA and RNA sequencing at baseline and optionally at progression will be described using figures representing the profiled patients. These figures will order patients by degree of response (PSA response for Cohort A and Cohort C; and RECIST response for Cohort B). A logistic model with response as the outcome may be used with specific markers as independent covariates to estimate an effect size if a profound pattern is seen. Differences seen in paired samples (baseline and progression) will be described individually and labeled as a responder/non-responder. Immune infiltration in tumor biopsies will be described using figures. Associations of the profiles with the response will be described using counts and proportions.

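### QoL questionnaires are not taken at the end-of-treatment visit, so patients who stop before C5D1 have no change score and the QoL results are at risk of bias from informative dropout

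*Combined protocol and SAP*

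**What the plan says.** QoL is a secondary objective and endpoint (Sections 2.2.4 and 2.5.4). In the Section 6.1 schedule, the row "QoL: BPI-SF and EORTC QLQ C30" is marked at screening and in the D1C5+ column every 12 weeks. Its cells for C1D1 to C4D1, EOT and Follow Up are empty.

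An EOT visit is planned for every patient: "End of Treatment Visit should occur within 3-4 weeks of last dose of protocol therapy". Another 12-weekly item does have an EOT collection: "Blood for research should be collected prior to study treatment on C1D1, C2D1, C3D1 and C5D1, every 12 weeks thereafter and end of treatment".

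After treatment, Section 5.6 says: "Patients will be followed every 3 months for 24 months after removal from treatment or until death, whichever occurs first". The Follow Up column of the schedule has survival status and PSA, but not QoL.

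Section 11.3 summarises the change from baseline at each later time point, overall and by cohort, and adds: "Each QoL change from baseline will be analyzed using a general linear model with repeated measures for an association with response". It does not say when response status is fixed for this model, and it gives no rule for missing questionnaires.

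**The concern.** The first QoL form after baseline comes only at C5D1. Treatment can end before that for reasons linked to how the patient is doing, and "Disease progression as defined in Section 7.0" is one of them. A patient who stops earlier has a baseline form and nothing to subtract from it.

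If such patients feel worse than those who continue, the reported QoL on therapy describes a selected group, and so does the comparison of responders with non-responders. The QoL population also differs from the response population: under Section 7.1, patients who progress before two PSA values are available still count as evaluable for PSA response. They can therefore count as non-responders in the response rate while being absent from the QoL model.

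Forms that were never collected cannot be recovered at analysis.

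**Working it through.** The documents give no sample size, effect or dropout figure for QoL, so there is no stated figure to reproduce.

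**Step 1. Time of the first form after baseline.** The cycle lengths come from the footnotes to the Section 6.1 schedule. C5D1 falls after four full cycles.
- Cohorts A and B: "1 cycle (C) = 21 days (D) for up to 4 doses of Nivolumab", so 4 × 3 weeks = week 12.
- Cohort C: "1 cycle (C) = 28 days (D) of Nivolumab monotherapy (480mg IV) for up to 104 weeks", so 4 × 4 weeks = week 16, if the D1C5+ column is taken literally.

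**Step 2. Patients without a change score.** The cohort sizes are 25, 15 and 25 (Section 11.1). The share stopping before C5D1 is not given. I assume 20-40%.
- Cohorts A and C, each: 0.20 × 25 = 5 to 0.40 × 25 = 10.
- Cohort B: 0.20 × 15 = 3 to 0.40 × 15 = 6.
- Whole trial: 13 to 26 of 65.

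The outcome in the model is change from baseline, so a repeated-measures model, even a likelihood-based one, has no outcome value for these patients.

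**Step 3. What this could do to the contrast (illustration; all QoL inputs are assumed).** Suppose mean change is 0 in responders and −10 in non-responders, with SD 20. Only non-responders stop early, a fraction f of them, and stopping has correlation ρ with worse QoL change. If 30% of 65 respond, baseline-only patients number 65 × 0.70 × f, about 9, 16 or 23 for f = 20%, 35% or 50%.

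The observed difference is 10 − 20 × ρ × φ(z) / (1 − f), where z is the (1 − f) quantile of the standard normal and φ its density. For f = 0.5 and ρ = 0.6: 10 − 20 × 0.6 × 0.399 / 0.5 = 0.4. A simulation with 400,000 draws per scenario gave the values below; the formula agrees to within about 0.1.

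| Correlation ρ | f = 20% | f = 35% | f = 50% |
|---|---|---|---|
| 0 | 10.1 | 10.0 | 10.0 |
| 0.3 | 7.8 | 6.6 | 5.2 |
| 0.6 | 5.8 | 3.1 | 0.4 |

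With forms from 70% of early stoppers, the observed difference is 9.1-9.4 at ρ = 0.3 and 8.3-8.9 at ρ = 0.6. With forms from all of them it is about 10. This treats the EOT form as equivalent to the missing C5D1 form. With no true difference, the same selection gives observed differences between 0 and −9.6.

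**Step 4. Timing of response.** Section 11.3 is silent, so the definitions elsewhere matter.
- Section 7.1.1 classifies a patient by a PSA decline of at least 50%, seen twice at least 3 weeks apart, with no fixed time. It also says benefit may take 12 weeks or longer to appear.
- Section 7.4.3 uses the best response up to progression, and CR or PR needs confirmation after more than 4 weeks. In Cohort B the first scheduled on-treatment scan and the first QoL form share the D1C5+ column. With scheduled scans alone, confirmed response is always established after the first QoL change.

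If these whole-course classifications enter the model as they stand, a later response is used to explain an earlier QoL value.

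**The case against.** The strongest case on the other side has four parts.

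- **Scope.** The objective is QoL in patients treated on protocol therapy, so on-treatment collection is defensible. The model is a secondary association with no threshold or decision attached. This stands, and it limits the importance of the point.
- **Early stopping for progression may be limited.** Scheduled scans start in the same column as QoL. Early PSA rises do not by themselves end treatment (Section 7.1.1), nor does PSA-only progression (7.1.2). Cohort B may continue beyond first progression (7.2), and nivolumab may continue after ipilimumab stops (5.2.1). This also stands in part. It leaves clinical or unscheduled progression, full discontinuation for toxicity, withdrawal and death. Death cannot be remedied by an EOT form.
- **Response can precede the first QoL form.** PSA is measured each cycle, so some PSA responses will be complete before C5D1. The time-order problem affects later PSA responders and confirmed RECIST responders, not everyone.
- **Attrition is partly visible.** Section 11.3 reports removals for adverse events and duration of therapy. That shows how many stopped, not how they felt.

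A reader might also infer that the plan models QoL against eventual response and that the result is biased, even dominated by selection. The documents do not support that. Section 11.3 does not state the timing of response; eventual response is the natural reading of Sections 7.1.1 and 7.4.3, but it remains an inference. Bias requires stopping to be related to QoL given response, and in the illustration the difference is undistorted when it is not.

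**Conclusion.** The collection gap is a fact of the schedule: no QoL at EOT or in follow-up, and therefore no change score for anyone who stops before C5D1. The empty EOT cell does not look like a table-reading artefact, because a footnote confirms in words that research blood is taken at end of treatment.

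The consequence is a risk of bias in QoL on therapy and in its association with response. Neither size nor direction can be found from the documents. The count of 5-10 of 25 and 3-6 of 15 rests on the assumed 20-40% early stopping. The illustration rests on assumed SD, effect and correlation, and on only non-responders stopping early. In that setting the contrast shrinks. Early toxicity stops among responders, or the time-order problem, could act differently.

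This is a minor point about a secondary endpoint. It is worth acting on because the missing forms cannot be recovered later. The primary response-rate conclusions do not depend on it.

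**What to change.** - **Section 6.1:** mark BPI-SF and EORTC QLQ-C30 at the EOT visit.
- **Section 11.3, data:** include the EOT forms in the change-from-baseline summaries and model at their actual time since start of treatment. State how missing forms are handled, and report the number of baseline-only patients by response.
- **Section 11.3, model:** enter response as a time-dependent covariate that switches on a stated date, for example when the confirming measurement is made, so that later response cannot explain earlier QoL.

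A week-12 landmark would not serve. Cohort A and B patients whose last dose is cycle 1, 2 or 3 (weeks 0, 3 and 6) have EOT at weeks 3-4, 6-7 or 9-10, so an analysis of QoL after week 12 would discard the very forms being added. It would also leave almost no confirmed responders in Cohort B.

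**Cost:** two questionnaires at an existing visit, a few lines of analysis text and slightly more analysis work. EOT forms come 3-4 weeks after the last dose, so they are not strictly on-treatment values and should be identified as such in the report.

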12.0 DATA AND SAFETY MONITORING

This study will be monitored in accordance with the NCI approved University of Michigan Rogel Cancer Center Data and Safety Monitoring Plan, with oversight by the Rogel Cancer Center Data and Safety Monitoring Committee (DSMC).

The Sponsor-Investigator (S-I)/Study Principal Investigator will provide ongoing monitoring of data and patient safety in this trial and conduct regular data review with participating sites

The Sponsor-Investigator (S-I)/Study Principal Investigator and/or the Project Manager/Delegate will review data and patient safety issues with participating sites per a defined quarterly meeting cadence. Depending on the protocol activity, the meeting cadence may be more frequent. This data review meeting may be achieved via a teleconference or another similar mechanism to discuss matters related to:

- Enrollment rate relative to expectations, characteristics of participants
- Safety of study participants (Serious Adverse Event & Adverse Event reporting)
- Adherence to protocol (protocol deviations)
- Completeness, validity and integrity of study data
- Retention of study participants

Participating sites are required to ensure all pertinent data for the review period are available in the database at the time of the discussion.

Participating sites unable to participate in the data review meeting are required to provide written confirmation that their site has reviewed the relevant data and patient safety issues for the review period and their site's data are in alignment with the data reported in the database. Written confirmation is to be provided to the Project Manager/Delegate within the timeline requested to retain compliance with monitoring timelines.

Documentation of the teleconference or alternate mechanism utilized to review items above is to be retained in the Trial Master File.

The Project Manager/Delegate is responsible for collating the data from all participating sites and completing the Protocol Specific Data and Safety Monitoring Report (DSMR) form to document the data review meeting discussion.

The DSMR will be signed by the Sponsor-Investigator (S-I)/Study Principal Investigator or designated Co-Investigator and submitted to the DSMC on a quarterly basis for independent review.

13.0 DATA MANAGEMENT

All information will be recorded locally and entered into Case Report Forms (CRFs) on the web-based electronic data capture (EDC) system of the University of Michigan. Online access will be provided to each site by the Coordinating Center.

CRFs will be reviewed and source verified by the MSC during annual monitoring visits and prior to and between visits. Discrepant, unusual and incomplete data will be queried by the MSC. The investigator or study coordinator will be responsible for providing resolutions to the data queries, as appropriate. The investigator must ensure that all data queries are dealt with promptly.

The data submission schedule is as follows:

- After subject enrollment
 - Subject Status
 - Demographics
- During study participation
 - All data should be entered online within 10 business days of data acquisition. Information on Serious Adverse Events must be entered within the reporting timeframe specified in Section 8 of the protocol.

All study information should be recorded in an appropriate source document (e.g. clinic chart).

14.0 QUALITY ASSURANCE AND AUDITS

The Data and Safety Monitoring Committee can request a 'for cause' quality assurance audit of the trial if the committee identifies a need for a more rigorous evaluation of study-related issues.

A regulatory authority (e.g. FDA) may also wish to conduct an inspection of the study, during its conduct or even after its completion. If an inspection has been requested by a regulatory authority, the site investigator must immediately inform the Coordinating Center that such a request has been made.

15.0 CLINICAL TRIAL MONITORING

Clinical studies coordinated by The University of Michigan Rogel Cancer Center must be conducted in accordance with the ethical principles that are consistent with Good Clinical Practices (GCP) and in compliance with other applicable regulatory requirements.

This study will be monitored by a representative of the Coordinating Center of the Rogel Cancer Center. Monitoring visits will be made during the conduct of the study and at study close-out.

Prior to subject recruitment, a participating site will undergo a site initiation meeting to be conducted by the Coordinating Center. This will be done as an actual site visit, teleconference, videoconference, or web-based meeting after the site has been given access to the study database and assembled a study reference binder. The site's principal investigator and his/her study staff should make every effort in attending the site initiation meeting. Study-related questions or issues identified during the site initiation meeting will be followed-up by the appropriate Coordinating Center personnel until they have been answered and resolved.

Monitoring of this study can include both 'Centralized Monitoring', the review of source documents at the Coordinating Center and 'On-site Monitoring', an actual site visit. The first 'Centralized' visit should occur after the first subject enrolled completes the first treatment cycle. The study site will send the de-identified source documents to the Coordinating Center for monitoring. 'Centralized' monitoring may be requested by the Coordinating Center if an amendment requires changes to the protocol procedures. The site will send in pertinent de-identified source documents, as defined by the Coordinating Center for monitoring.

The first annual 'On-site' monitoring visit should occur after the first five study participants are enrolled or twelve months after a study opens, whichever occurs first. The annual visit may be conducted as a 'Centralized' visit if less than three subjects have enrolled at the study site. The type of visit is at the discretion of the Coordinating Center. At a minimum, a routine monitoring visit will be done at least once a year, or once during the course of the study if the study duration is less than 12 months. The purpose of these visits is to verify:

- Adherence to the protocol
- Completeness and accuracy of study data and samples collected
- Proper storage, dispensing and inventory of study medication
- Compliance with regulations

During a monitoring visit to a site, access to relevant hospital and clinical records must be given by the site investigator to the Coordinating Center representative conducting the monitoring visit to verify consistency of data collected on the CRFs with the original source data. While most patient cases will be selected from patients accrued since the previous monitoring visit, any patient case has the potential for review. At least one or more unannounced cases will be reviewed, if the total accruals warrant selection of unannounced cases.

The Coordinating Center expects the relevant investigational staff to be available to facilitate the conduct of the visit, that source documents are available at the time of the visit, and that a suitable environment will be provided for review of study-related documents. Any issues identified during these visits will be communicated to the site and are expected to be resolved by the site in a timely manner. For review of study-related documents at the Coordinating Center, the site will be required to ship or fax documents to be reviewed.

Participating site will also undergo a site close-out upon completion, termination or cancellation of a study to ensure fulfillment of study obligations during the conduct of the study, and that the site Investigator is aware of his/her ongoing responsibilities. In general, a site close-out is conducted during a site visit; however, site close-out can occur without a site visit.

17.0 APPENDICES

APPENDIX A

ECOG Performance Status Scale	
Grade	Description
0	Normal activity. Fully active, able to carry on all pre-disease performance without restriction.
1	Symptoms but ambulatory. Restricted in physically strenuous activity, but ambulatory and able to carry out work of a light or sedentary nature (e.g., light housework, office work).
2	In bed <50% of the time. Ambulatory and capable of all self-care, but unable to carry out any work activities. Up and about more than 50% of waking hours.
3	In bed >50% of the time. Capable of only limited self-care, confined to bed or chair more than 50% of waking hours.
4	100% bedridden. Completely disabled. Cannot carry on any self-care. Totally confined to bed or chair.
5	Dead.

APPENDIX B

Brief Pain Inventory (Short Form)

STUDY ID #: _____

DO NOT WRITE ABOVE THIS LINE

HOSPITAL #: _____

Brief Pain Inventory (Short Form)

Date: _____ / _____ / _____

Time: -----

Name: _____

First

[figure not shown]
Middle Initial

1. Throughout our lives, most of us have had pain from time to time (such as minor headaches, sprains, and toothaches). Have you had pain other than these everyday kinds of pain today?

1. Yes

2. No

2. On the diagram, shade in the areas where you feel pain. Put an X on the area that hurts the most.

3. Please rate your pain by circling the one number that best describes your pain at its worst in the last 24 hours.

4. Please rate your pain by circling the one number that best describes your pain at its least in the last 24 hours.

0 1 2 3 4 5 6 7 8 9 10
No Pain Pain as bad as
Pain you can imagine

5. Please rate your pain by circling the one number that best describes your pain on the average.

A horizontal scale from 0 to 10. The numbers 0, 1, 2, 3, 4, 5, 6, 7, 8, 9, and 10 are evenly spaced along the top. Below the scale, the text "No Pain" is centered above the number 0, and the text "Pain as bad as you can imagine" is centered above the number 10.

6. Please rate your pain by circling the one number that tells how much pain you have right now.

A horizontal scale from 0 to 10. The numbers 0, 1, 2, 3, 4, 5, 6, 7, 8, 9, and 10 are evenly spaced along the top. Below the scale, the text "No Pain" is centered under the number 0, and the text "Pain as bad as you can imagine" is centered under the number 10.

STUDY ID #: _____ DO NOT WRITE ABOVE THIS LINE HOSPITAL #: _____

Date: _____ / _____ / _____
Name: _____

Time: _____

Last

First

Middle Initial

7. What treatments or medications are you receiving for your pain?

8. In the last 24 hours, how much relief have pain treatments or medications provided? Please circle the one percentage that most shows how much relief you have received.

0% 10% 20% 30% 40% 50% 60% 70% 80% 90% 100%
No Relief Complete Relief

9. Circle the one number that describes how, during the past 24 hours, pain has interfered with your:

A. General Activity

0 1 2 3 4 5 6 7 8 9 10
Does not Interfere Completely Interferes

B. Mood

0 1 2 3 4 5 6 7 8 9 10
Does not Interfere Completely Interferes

C. Walking Ability

0 1 2 3 4 5 6 7 8 9 10
Does not Interfere Completely Interferes

D. Normal Work (includes both work outside the home and housework)

0 1 2 3 4 5 6 7 8 9 10
Does not Interfere Completely Interferes

E. Relations with other people

0 1 2 3 4 5 6 7 8 9 10
Does not Interfere Completely Interferes

F. Sleep

0 1 2 3 4 5 6 7 8 9 10
Does not Interfere Completely Interferes

G. Enjoyment of life

0 1 2 3 4 5 6 7 8 9 10
Does not Interfere Completely Interferes

Copyright 1991 [name]
Pain Research Group
All rights reserved

